BM cytology assessment (local) ¹⁰			x					x ¹⁴	x ¹⁵
Serum chemistry (local)	x		x		x		x	x	x
Automated CBC (local)	x	x	x	x	x	x	x	x	x
Cytogenetics (local)			x					x	

Part 2c – extension treatment phase, from cycle 5 (non-responders with stable or controlled disease who continue treatment at the investigator's discretion)

VISIT NO.	██████████
Study Day (± 3d)	████████████████████
Study Week	██████
Cycle	██████████
Concomitant MDS/AML specific medication	X
Pregnancy test	X
Imetelstat administration and drug account	X ¹⁶
Toxicity/AE assessment	X
LOCAL LABORATORY: Response assessment ¹⁷	X ¹⁸
CBC with differential (local)	X ¹⁸
PB blast assessment (local)	X ¹⁸
BM cytology assessment (local)	X ¹⁸

¹⁶ The dosing frequency for imetelstat (every ■ weeks or every ■ weeks) for these subjects will be determined at the discretion of the investigator.

17 Response assessment will be performed based on the combined response assessment criteria for MDS and AML based on IWG 2018 criteria (MDS) and the criteria of the European LeukemiaNet (AML). Additionally, the BM blast level at each response assessment will be the basis for deciding the frequency of treatment of imetelstat (every █ weeks or every █ weeks) until the next response assessment.

¹⁸ Optional response assessment and lab measurements to be done according to standard of care and/or only in case needed to assess and follow-up on (S)AEs and dose modifications

Part 3 – EOT and follow-up period (all patients)

VISIT NO.	██████ ██████ ██████	████ ██████ ██████	██████████ ██████ ██████████ ██████████	██████	██████████
Study Day (± 3d)	██████	██████	██████	██████████	██████████
Study Week	██████	██████	██████	██████	██████
Informed consent					
In- / exclusion criteria ³					
MDS/AML related medical history					
Concomitant MDS/AML specific medication	x	x	x	x	
Physical examination, vitals	x	x	x	x	
BMI	x	x	x	x	
Pregnancy test ⁴	x	x	x	x	
Toxicity/AE assessment	x	x	x	x	
Quality of life (QoL, EORTC QLQ-C30)	x	x	x		
Information on current state of condition / survival status	x	x	x	x	x
Central assessments / correlative analyses (EU: Leipzig, AUS: QIMRB, Brisbane)					
Bone marrow aspiration (5 mL sodium heparinized in separate tubes for central assessments)		x ²²			
Peripheral blood sampling for central assessments (10 mL sodium heparinized blood in separate tubes for central assessments)		x ²²			
Genetic profiling (NGS) at central laboratories		x			
MRD analyses at central laboratories					

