5.1.3 Disease assessments in the primary phase of the treatment period (■■■■■)

After cycles ■ and ■ (i.e., at the beginning of cycles ■ and ■) response assessments will be carried out based on bone marrow and peripheral blood samples taken. For that, blood counts to assess potential cytopenias will be carried out and bone marrow and peripheral blood smears will be prepared to perform cytomorphology assessments.

Of these response assessments, the assessment at the end of ■■■■■ (performed at the beginning of cycle 5) is the primary endpoint (pEP) assessment.

Based on the outcome of the disease assessment in ■■■■■, if signs of disease progression are seen in the bone marrow, treatment with imetelstat will be stopped and the patient will undergo EOT and enter the follow-up phase.

Based on the outcome of the pEP (■■■■■) visit disease assessment, subjects will be either discontinued from treatment with imetelstat and enter the posttreatment follow-up phase (non-responders) or will continue treatment with imetelstat until loss of response/disease progression in the extension phase of the treatment period (responders) (see below at 5.1.4). In the absence of alternative treatment options, non-responders with stable or controlled disease may continue treatment in the extension phase at the investigator's discretion, in consultation with the sponsor, provided the disease remains controlled and none of the discontinuation criteria as described in section 7.7 are met. These subjects will follow the assessments and procedures according to the schedule of assessments for the extension phase (section VII, Part 2c). Responders who have BM blasts $\geq 5\%$ at the response assessment in cycle ■ will continue to receive imetelstat every ■ weeks. Responders who have BM blasts $<5\%$ at the response assessment in cycle ■ will continue to receive imetelstat every ■ weeks.

The disease assessment will be performed according to combined response criteria based on IWG 2018 criteria (MDS)¹ and the criteria of the European LeukemiaNet (AML)² in order to harmonize the criteria for MDS and AML patients in this trial. The combined criteria are listed in Appendix III a), section 16.3.

- Evidence of clinical benefit is defined as:
 - **At least partial remission (PR):**
 - This includes CR, CRi, PR and HI (any line) as per the combined response criteria used in this trial

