All subjects will receive a starting dose of [REDACTED]. All subjects will be treated for at least [REDACTED] cycles, followed by a response assessment according to combined response criteria based on IWG 2018 criteria (MDS)¹ and the criteria of the European LeukemiaNet (AML)² (see Appendix III a), section 16.3). Subjects exhibiting a response and have BM blasts \geq 5% at the time of the response assessment after [REDACTED] treatment cycles will continue to receive imetelstat every [REDACTED] weeks until loss of response/disease progression. Patients who are categorized as responders and have BM blasts $<$ 5% at the response assessment will continue to receive imetelstat every [REDACTED] weeks until loss of response/disease progression. For patients exhibiting a response to treatment, each disease assessment after cycle [REDACTED] will also determine the frequency of imetelstat treatment ([REDACTED]) based on BM blast levels. Non-responding patients at the time of the response assessment after 4 treatment cycles will discontinue imetelstat treatment, undergo EOT and enter the follow-up phase of the trial. In the absence of alternative treatment options, non-responders with stable or controlled disease may continue treatment at the investigator's discretion, in consultation with the sponsor, provided the disease remains controlled and none of the discontinuation criteria as described in section 7.7 are met. These subjects will follow the assessments and procedures according to the schedule of assessments for the extension phase (section VII, Part 2c).

If signs of disease progression are present in bone marrow after [REDACTED] doses with imetelstat (at the early disease assessment in [REDACTED]), treatment with imetelstat must be discontinued and the patient undergoes EOT.

Imetelstat dose delay or reduction for Grade 3 or Grade 4 toxicity will be instituted as needed, per the instructions provided in Table 1, Table 2, Table 3, and Table 4. Note that these instructions are intended for Grade 3 or Grade 4 toxicities observed at the time of the next planned dose. These instructions are not applicable when toxicities occur between doses and subsequently resolve to Grade $<$ 3 by the time of the next planned dose.

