7.2.2.1 Safety of Imetelstat as Monotherapy in Hematologic Malignancies

Cytopenias, particularly thrombocytopenia and neutropenia, are the primary dose limiting toxicities (DLTs) identified with imetelstat. The frequency and severity of all cytopenias, particularly thrombocytopenia and neutropenia, are associated with the imetelstat dose intensity (actual dose and frequency of dosing); however, cytopenias are manageable through dose modifications, reversible and of short duration, and with limited clinical consequences, for example febrile neutropenia.

Completed Monotherapy Studies in Hematologic Diseases

[REDACTED]

Ongoing Study 63935937/MDS3001 (NCT02598661) in Low- or Intermediate-1 Risk MDS

Treatment with imetelstat was generally well tolerated and consistent with the existing safety profile. The most common TEAEs (cytopenias) were predictable and manageable, and for the majority of events in Part 1 these were reversible.

[REDACTED]

For complete safety information on imetelstat please refer to current Investigator's Brochure provided in the context of this protocol.

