8.1.3 Treatment period

The subject will start treatment upon confirmation of eligibility. The subject must start treatment within [REDACTED] of signing the ICF. If screening assessments are performed within 72 hours of C1D1, serum chemistry laboratory assessments and physical examinations need not be repeated at C1D1 with the exception of automated CBC.

If subject completed the QoL EORTC QLQ-C30 questionnaire at Screening within 2 weeks of C1D1, it does not have to be repeated at C1D1. If performed on C1D1, it should be completed prior to IMP administration.

On dosing days, local laboratory levels should be assessed prior to each IMP administration to ensure dose modification rules are followed as outlined in section 7.3 Dose modification guidelines.

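### Part 2c lets continuing non-responders be dosed with no scheduled serum chemistry or automated CBC and only as-needed counts and disease assessment, which does not fit sections 5.1.3, 7.1/7.3, 7.7 and 8.1.3

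*Protocol*

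**What the plan says.** Part 2c of the schedule (protocol section VII, repeated in SAP 2.4) is for "non-responders with stable or controlled disease who continue treatment at the investigator's discretion". Protocol 5.1.3 and 7.1 both direct these patients to it, so it is their governing schedule.

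Part 2c has eight rows. Concomitant disease-specific medication, pregnancy test and toxicity/AE assessment carry a plain mark. Imetelstat administration carries footnote 16. Response assessment, CBC with differential, peripheral blast assessment and marrow cytology carry footnote 18, which opens with "Optional response assessment and lab measurements to be done according to standard of care". Its second limb, offered as an addition or an alternative to the first, has them done "only in case needed to assess and follow-up on (S)AEs and dose modifications".

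The body text says:

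- **8.1.3:** on dosing days, "local laboratory levels should be assessed prior to each IMP administration", so that the dose modification rules can be followed. Section 8.1 counts the extension phase as part of the treatment period.
- **7.1:** on dose delay and reduction, "these instructions are intended for Grade 3 or Grade 4 toxicities observed at the time of the next planned dose".
- **7.2.2.1:** "Cytopenias, particularly thrombocytopenia and neutropenia, are the primary dose limiting toxicities (DLTs) identified with imetelstat". The list of tables gives Table 3 as covering liver function test elevations.
- **5.1.3:** continuation is allowed "provided the disease remains controlled and none of the discontinuation criteria" in 7.7 are met. Section 7.7 includes progression by the combined criteria.
- **8.1.6:** each disease assessment in the extension phase should confirm that progression is absent.

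**The concern.** The patients concerned did not meet the response definition but are still being dosed. The drug's stated dose-limiting toxicities are found in a blood count, and one dose-modification table depends on liver tests. A site that works only from Part 2c has no scheduled test to show either problem before the next infusion. It also has no scheduled assessment to show that the condition for continuing is still met. A site that works from 8.1.3 would test before each dose. Two sites could therefore treat the same kind of patient differently, and each could point to the protocol.

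There is a smaller consequence for the analysis. SAP 7.7.6 takes progression from the response assessment and censors patients without an event at the last observation. Where response assessment is optional, a patient can keep adding progression-free time by attending for dosing alone.

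**Working it through.** No calculation applies; the check sets the texts side by side and counts schedule marks.

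**1. Which schedule governs.** Sections 5.1.3 and 7.1 say these patients will follow Part 2c. Section 8.1.3 applies to the treatment period, which 8.1 says includes the extension phase, and it does not exempt Part 2c. Both apply, and the protocol does not say which prevails.

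**2. What each part schedules**, counting columns marked:

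| Part | Dosing | Automated CBC | Serum chemistry | Dosing columns without chemistry |
|---|---|---|---|---|
| 1 | 10 of 11 | 11 of 11 | 6 of 11 | 5 (columns 3, 5, 7, 9, 11) |
| 2a | 5 of 9 | 9 of 9 | 6 of 9 | 0 |
| 2b | 9 of 9 | 9 of 9 | 6 of 9 | 3 (columns 2, 4, 6) |
| 2c | its single column | no row | no row | no row |

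Physical examination and vitals are marked in every column of Parts 1, 2a and 2b and have no row in 2c. Section 8.2.1.1 places weight on dosing days within that examination, and 7.1 has the dose recalculated when weight changes by 10% or more.

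**3. Footnote 18 against 8.1.3.** The footnote sets an as-needed rule; 8.1.3 sets a routine one, worded as should. The as-needed rule keeps testing available for dose modification. However, low neutrophils, low platelets or raised liver tests at the next planned dose are ordinarily learned from the test itself, so the need may not be known until the test is done. The footnote is attached to no chemistry row, because none exists.

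**4. Footnote 18 against 5.1.3 and 7.7.** Progression under the combined criteria (Appendix III a) rests largely on marrow and peripheral blasts. Those measurements are optional in Part 2c, so the condition for continuing may go unchecked.

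**5. Footnote 16 against footnote 17.** Footnote 16 leaves dosing frequency to the investigator's discretion. Footnote 17 bases it on the marrow blast level at each response assessment, an assessment that footnote 18 makes optional. Both are in the same table.

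**6. Censoring.** SAP 7.7.6 censors PFS at the last observation, and protocol 2.3.2 at the last follow-up visit. SAP 7.7.7 censors duration of response at the last response assessment. The two response-based time endpoints therefore use different rules.

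**The case against.** The strongest reply is that footnote 18 does not forbid testing. It allows standard-of-care tests and tests needed for adverse events and dose modifications, which is the purpose 8.1.3 gives. Toxicity/AE assessment is unqualified in Part 2c, and 8.1.7 requires repeat laboratory tests once a dose is delayed for a laboratory abnormality or an adverse event. This much stands: a reader might infer that the footnote is the opposite of 8.1.3, or that the dose-modification tables cannot be applied at all, and the text supports neither. It does not remove the conflict between as-needed and routine testing, and 8.1.7 operates only after a problem has been found.

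A second reply is that missing chemistry on a dosing day is not peculiar to Part 2c. That is correct: Part 1 has five such columns and Part 2b three, and 8.1.3 does not name chemistry. What is particular to Part 2c is that chemistry and automated CBC have no row at all and the remaining counts are optional.

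A third reply concerns PFS. Protocol 5.1.4 and 8.1.6 say data on these patients may be collected without affecting the statistical analyses, and 10.12 places data from continued treatment outside the trial. The SAP sections on the FAS, PFS and safety set no exclusion or cut-off that would achieve this, so whether Part 2c data enter PFS is unsettled. A bias in PFS is possible but not shown.

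**Conclusion.** The inconsistency is in the current text of both documents and should be resolved, because it concerns monitoring of patients who are still being dosed. It is a conflict between a routine and an as-needed rule, with rows missing from one table, and a second conflict between footnotes 16 and 17. The redacted visit, day and dose cells do not affect it.

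Its size in patients is not known. The SAP's document history reports no responders at the interim analysis, and a reader might infer that continuing non-responders will be most or all of the extension phase. The documents do not support that: the interim result belongs to the earlier, less frequent regimen, the second cohort is dosed differently, and no count of continuing non-responders is given.

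For PFS, later or missed detection of progression would tend to lengthen the estimate if these data are analysed, but by an amount that cannot be calculated here. Censoring would not correct cases where progression was missed and the patient later died, since those are already events dated at death.

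**What to change.** Reconcile Part 2c and footnotes 16 to 18, in the protocol and in the SAP 2.4 copy, with protocol 5.1.3, 7.1/7.3, 7.7, 8.1.3 and 8.1.6. State which text prevails for laboratory tests before dosing, for disease assessment and for dosing frequency in this group. Which monitoring rule applies is for the sponsor to decide. If Part 2c is meant to be an exception, 8.1.3 should say so; if not, the table should carry the missing rows. The cost is a table and footnote correction in the next amendment and the same edit in the SAP.

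Treat PFS censoring as a separate change. If the sponsor alters it, censor at the last adequate disease assessment for every patient in SAP 7.7.6, following the approach 7.7.7 takes for duration of response, and align protocol 2.3.2. A rule for the Part 2c group alone would give two PFS definitions within one cohort, split by a response observed after baseline. The SAP should also say whether Part 2c data enter the efficacy and safety tables. This takes a few sentences.

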1.1 Introduction

1.1.1 Myelodysplastic syndromes (MDS) and acute myeloid leukemia (AML)

Myelodysplastic syndromes constitute a heterogeneous form of blood cancer that primarily affects the elderly and are characterized by anemia and other cytopenias and a high risk of leukemic transformation³. In routine clinical practice, MDS are suspected when an otherwise unexplained anemia is associated with other cytopenias, increased mean corpuscular volume, or increased red cell distribution width. Diagnosis requires bone marrow examination and cytogenetic studies. The bone marrow is typically hyperproliferative. The diagnosis is based on demonstration of erythroid, granulocyte, or megakaryocyte dysplasia in 10% or more of informative cells⁴. The natural history of MDS includes transformation to AML in a proportion of patients.

Especially for patients with higher risk MDS there is an increased risk of progression to AML. The transition between the two diseases is often fluent and, as a main criterion, based on the percentage of blasts in bone marrow (BM) or peripheral blood (PB) with $\geq 20\%$ blasts being a cut-off defining AML⁴. Due to the similar biology of higher risk MDS and AML, treatment options are comparable. Prognosis for both diseases is dismal, especially in patients who are not eligible for allogeneic hematopoietic stem cell transplant (allo-HSCT), the only curative treatment option.

The hypomethylating agent (HMA) 5-azacytidine ((AZA) has been approved for MDS in Europe and Australia based on the results of the MDS AZA-001 trial⁵. The overall response rate (ORR) ranges between 25% and 40%, and there is a significant reduction of the risk of progression to AML. A 7-day regimen of IV/SC AZA at 75 mg/m² every 28 days demonstrated a 9.5 month OS benefit in patients with higher risk MDS based on IPSS in comparison with conventional care options⁵⁻⁹. Subsequent real-world data have nuanced these results with lower benefits of HMA compared with the original studies, which might be due to differences in adherence to dosing schedules, treatment duration, and less rigorous patient selection compared with the landmark clinical trials^{10,11}.

For patients progressing on HMA therapy, the prognosis is poor, with a median OS of 4-5.6 months for higher risk MDS patients^{12,13} and there are very limited options for these patients, especially if they are not eligible for intensive chemotherapy or allo-HSCT.

Lately, the approval of the combination of AZA and venetoclax (VEN) has added benefits to the treatment of patients with HR MDS or AML not eligible for intense chemo or stem cell transplantation. The combination demonstrated improvements of response and survival rates especially in elderly or comorbid AML patients compared to single-agent AZA (CR/Cri of 66.4% vs. 28.3% and OS of 14.7 vs. 9.6 months)¹⁴. However, new and complementing treatment options in this vulnerable patient population not responding or relapsing are still urgently needed.

1.1.2 Telomeres and Telomerase

There is evidence that perturbations of telomere homeostasis are implicated in the pathogenesis of myeloid disorders, including MDS and AML¹⁵. Telomeres are structural elements of non-coding DNA acting as protective caps at the ends of chromosomes thereby preventing erosion of genomic DNA during cell division. Telomeres shorten with each round of cell division and specific mutations in telomere repair complex (TERT, TERC and associated proteins) can also lead to telomere attrition, eventually leading to replicative exhaustion and/or genomic instability. Proper telomere maintenance is of particular functional relevance in cellular compartments with high baseline cellular turnover such as the hematopoietic (stem cell) compartment. Telomere loss is prevented by the presence of the enzyme telomerase, which consists of 2 essential components: the human telomerase ribonucleic acid (RNA) template (hTR) and the human telomerase reverse transcriptase (hTERT) catalytic subunit. Telomerase counters telomere loss by the addition of TTAGGG repeats to the chromosome ends¹⁶. hTERT is overexpressed in MDS and AML^{17,18} suggesting that targeting telomere length might be a valuable strategy to explore new treatment options in these two entities.

1.2 Imetelstat and rationale of the study

Imetelstat (GRN163L) is a covalently-lipidated 13-mer thiophosphoramidate oligonucleotide that acts as a potent specific inhibitor of telomerase. Telomerase inhibition leads to loss of a cancer cell's ability to maintain telomere length (TL), resulting in cell-cycle arrest, apoptosis, or senescence. Imetelstat binds with high affinity to the template region of the RNA component of hTERT and is a competitive inhibitor of telomerase enzymatic activity^{19,20}. Treatment of various cancer cells with imetelstat in vitro increases their sensitivity to radiation, decreases their clonogenic potential, and results in altered expression of stem-cell related genes^{21,22}.

Data from a phase II study investigating imetelstat in lower risk MDS patients with red blood cell (RBC) transfusion dependency show 8- and 24-week RBC transfusion independency (TI) rates of 37% and 23%, respectively, with a median TI duration of 65 weeks in the overall population (n=57). In a subset population of HMA and lenalidomide-naïve patients, 8- and 24-week RBC TI rates were 42% and 29%, respectively, with a median TI duration of 86 weeks. Cytogenetic and mutational data revealed a reduction of the malignant clones, suggesting disease modification activity. These encouraging results in lower risk MDS provide an encouraging basis for further investigation of the agent in higher risk MDS and AML patients ineligible for allo-HSCT, constituting entities with an even greater need for new therapeutic options²³.

1.3 Risk benefit assessment

There are currently very few licensed drugs in the EU to treat MDS or AML patients having failed or being refractory to treatment with HMAs. Furthermore, allo-HSCT can be offered only to a minority of those patients. Therefore, new treatment options are urgently needed for this patient cohort.

Imetelstat, a first-in-class telomerase inhibitor, with its novel mechanism of action, may provide clinical benefit to MDS and AML patients. First clinical trial results suggest an activity in lower risk MDS and good tolerability²³. The main side effects were thrombocytopenia and

neutropenia which were reversible in the majority of the patients. It is expected that this can be also managed effectively in the current patient population.

